6. OBJECTIVES AND OUTCOME MEASURES

Objectives	Outcome Measures	Timepoint(s) of outcome measure
Primary Objectives		
Feasibility of study	Ability to recruit planned participant number and carry out scheduled experiments in reproducible fashion	
 Analyses post-study completion Some evidence during interim analyses per group
Effect of stimulation on sleep stages	EEG changes (frequency changes, changes in EEG patterns and sleep structure)	
 During stimulation Post-stimulation at specific sleep stages

Secondary Objectives
 
Effect of stimulation on sleep inertia and vigilance & performance during the day
 
Controlling sleep depth and sleep-wake transitions
	
Performance on short and long test battery (see section 9.6.3)
 
Assessment of effect on latency to sleep onset and REM sleep, number of sleep cycles, duration of sleep stages, number of awakenings per night, sleep efficiency
	
 Upon awakening (post-baseline night and post-intervention) During the day (post-baseline and intervention) During intervention nights

Tertiary Objectives
 
Effect of stimulation on other measures of arousal
	
Effect on autonomic measures such as heart-rate variability and blood pressure, as well as salivary cortisol levels
	
 Overnight measurements Salivary cortisol levels measured upon awakening each day (6am).

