We will use a combination of subjective and objective measurements of sleep quality and efficiency to measure the impact of any sleep perturbations. The following objective metrics will be derived from visual/manual polysomnography (gold standard) & automated algorithm sleep staging:

1. Total sleep time.
2. Number of sleep cycles (switches of non-rapid eye movement (NREM) and rapid eye movement (REM) sleep).
3. Initial sleep and REM latencies (Time from beginning of study to the first stage of sleep, and from beginning of sleep to first REM sleep onset).
4. Duration of N1, N2, N3, and REM stages, and the duration of NREM (sum of N1,N2,N3)stages.
5. Sleep efficiency (100*total sleep time/time in bed).
6. Number of awakenings during night, including arousals per hour and duration of time spent awake after initial sleep onset (i.e., wake after sleep onset time)
7. Apnea-hypopnea and respiratory disturbance indices (the frequency of stop or reduced breathing episodes, and respiratory arousals per hour)
8. Periodic limb movement indices (the frequency of periodic leg movements of sleep per hour)
9. Measures of arousal during sleep
 - a. behavioural macrostate observations such as eye opening or blinking that can be assessed in video recordings

- b. microarousal observations defined exclusively by cortical fast frequency shifts (ie, >14 Hz rhythms) lasting 3 seconds or longer, with or without added autonomic measures of tachycardia.
 - c. Spectral composition of the sleep stage specific EEG over the 0.25-32 Hz frequency range
 - d.
10. Salivary samples to characterize awakening levels of cortisol will be obtained in the morning (~6AM) at the end of each night.
- 11.
12. Questionnaires will be administered to patients as per the list below:
 - Upon enrollment/prior to their visit:
 - The following questionnaires or tasks will be administered to or completed by both the Epilepsy and Parkinson's disease Cohort at specified time points (see schedule of events)
1. Neurological Exam & Mini-Mental State Examination (MMSE).
2. Current medications and medication history. Medications will be kept stable
3. Mood assessment with Beck Inventory for Anxiety and Depression
4. Quality of life evaluation (QOLIE-31) questionnaire.
5. Patient sleep diary (bedtime, awakening time, arousals/sleep disturbances, perceived sleep quality).
6. Karolinska Sleepiness Scale (KSS) (Akerstedt and Gillberg, 1990).
7. Profile of Mood States Scale (POMS) (McNair, Lorr and Doppleman, 1971)

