9.5. Blinding and code-breaking

There will be no blinding in the study and therefore no code-breaking procedure is required.

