9.6. Description of study intervention(s), comparators and study procedures (clinical)

9.6.1. Description of study intervention(s)

We will use both an open and a closed-loop approach to investigate sleep perturbations through stimulation deep brain targets. As previously mentioned, FDA approved clinician or patient programmers specific to the implanted device will be used at the open-loop stage, to explore the effect of available stimulation patterns when they are synchronized with different sleep stages. A physician/sleep technician team will be overseeing the delivery of stimuli during real-time sleep scoring on testing nights. See Appendix A. for example stimulation paradigms

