11.2. Description of the Statistical Methods

All analyses will be performed using commercially available software including MATLAB and SPSS. We will use a combination of novel techniques as well as existing and previously published approaches to signal analysis of EEG data, classification and testing for statistical significance. Parametric and non-parametric statistical testing procedures may be employed.

A Hidden Markov Model (HMM) can be generated for each patient, to assist in a statistical comparison of the effect of electrical perturbation of the brain. HMM states will be based on observations made by currently utilized metrics, such as EEG activity in different frequency bands, while the algorithm used for HMM will be based on literature (Vidaurre et al. 2018). A Hidden Markov Model (HMM) will be updated for each disease state, and patient, to add additional data for the stimulation matrix.

We will further assess correlations between stimulation perturbations and observed cognitive measures, physiological biomarkers (cortisol), subjective questionnaires, and post-hoc analysis of sleep patterns. Comparisons between patients control nights will provide a general assessment of in-patient variability. With the limited dataset, areas of statistical significance will be assessed. Where statistical analysis is not possible, consistency and data trends will be evaluated.

Outcomes (primary, secondary, tertiary) have been described in section 6 page 14, while comparators and interventions described in section 9.6 page 20.

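### Section 9.5 rules out all blinding, so manually staged sleep outcomes may be scored by people who know the night, the stimulation pattern and the hoped-for effect

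*Combined protocol and SAP*

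**What the plan says.** Section 9.5 is one sentence: "There will be no blinding in the study and therefore no code-breaking procedure is required". It does not separate delivering stimulation from scoring outcomes.

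Section 7 introduces the sleep metrics as follows: "The following objective metrics will be derived from visual/manual polysomnography (gold standard) & automated algorithm sleep staging". Two staging methods are named. The plan does not say which one governs the analysis or what happens when they disagree. Section 7 also commits to AASM scoring rules and provides for anonymized data to be shared between sites for analysis.

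Section 9.6.1 describes the testing nights: "A physician/sleep technician team will be overseeing the delivery of stimuli during real-time sleep scoring on testing nights". Section 9.7 adds that the sleep monitor, site clinician and scientist make the manual interventions in the initial sleep cycles.

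Under section 11.5, the PI and sleep scientist team use the baseline night to choose stimulation timing and to form expectations about the effects they want. Analyses after the first visit then judge how far those expectations were met, and the second visit builds on the result.

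Section 6 lists "Effect of stimulation on sleep stages" as a primary objective beside feasibility. Its outcome measure has three parts: frequency changes, EEG-pattern changes and sleep structure. The secondary outcomes include "Assessment of effect on latency to sleep onset and REM sleep, number of sleep cycles, duration of sleep stages", awakenings and sleep efficiency. Section 11.2 mentions a "post-hoc analysis of sleep patterns" but names no scorer, masking or agreement check.

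**The concern.** Manual staging needs judgement at stage boundaries and in calling arousals and awakenings. A scorer who knows which night is on screen, what stimulation was given and what effect was hoped for may resolve borderline epochs in the expected direction. Such an error is systematic, so more epochs or more patients do not average it out.

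The plan's main comparisons are within patient: usual settings, stimulation off, and the various patterns set against each other (section 9.6.2). A tilt that differs by condition goes straight into those contrasts. Because first-visit results guide second-visit stimulation, it could also carry forward. Open delivery is unavoidable here, but that is no reason to leave the later reading of stored recordings unmasked.

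**Working it through.** **Which steps need to be open**

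| Step | Must the person know the condition? | Source |
|---|---|---|
| Delivering stimulation | Yes | 9.6.1, 9.7 |
| Real-time staging that triggers it | Yes | 9.6.1, 9.7 |
| Manual scoring of stored recordings as outcome | No | Not described; 9.5 makes no exception |

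**Which outcomes are exposed (section 6)**

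- Primary, feasibility: not exposed.
- Primary, frequency and EEG-pattern changes: where computed, exposed only through the staging used to assign epochs to stages.
- Primary, sleep structure: directly exposed where staged manually.
- Secondary, stage durations, latencies, cycles, awakenings and efficiency: directly exposed where staged manually.

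**Size in minutes (assumption only)**

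The documents give no estimate of scoring bias, no epoch length and no night length. Assume 30-second epochs (120 per hour), a night of 6-8 hours, and a share of 2-5% of epochs relabelled in one direction into or out of one stage, on one side of the contrast.

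Shift in minutes = hours × 120 × share × 0.5.

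- 6 h, 2%: 720 × 0.02 × 0.5 = 7.2
- 8 h, 2%: 960 × 0.02 × 0.5 = 9.6
- 6 h, 5%: 720 × 0.05 × 0.5 = 18
- 8 h, 5%: 960 × 0.05 × 0.5 = 24

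The range is about 7-24 minutes of apparent change in a stage with no true effect. If the same tilt applied to both nights it would cancel. If it ran in opposite directions it would add.

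**Size in false-positive rate (illustration only)**

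The plan's own figure reproduces: a minimum of 3 patients × 5 locations = 15 (section 11.3). Section 11.3 says effect sizes are unknown, and no SD, numerical alpha or power is given. Assume a two-sided paired t-test at 0.05, no true effect, and a scoring shift of b standard deviations of the within-patient difference. The test statistic is then noncentral t with n − 1 degrees of freedom and noncentrality b√n. For example, 0.5 × √15 = 1.94.

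| b | n = 3 (one location) | n = 15 (pooled) |
|---|---|---|
| 0 | 5.0% | 5.0% |
| 0.2 | 5.6% | 11.2% |
| 0.5 | 8.4% | 43.8% |
| 0.8 | 13.5% | 82.1% |

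Without an SD, the minutes cannot be converted to b. The table shows only that a fixed shift does more harm as n grows. Masking leaves n unchanged, and complete masking would set b to 0.

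**The case against.** The best reply is that this is an exploratory, open-label feasibility study with partial safeguards. AASM rules narrow the room for judgement, and automated staging is already planned beside manual scoring. Both points stand as mitigation. Neither closes the gap: the rules leave borderline epochs to judgement, manual scoring is labelled the gold standard, and no rule settles disagreement between the two methods. The plan also names an effect objective as primary and intends significance testing (sections 11.2 and 11.7).

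A reader might infer several stronger things that the documents do not support:

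- **The bedside team will score the outcomes.** The plan never says who scores them. The expectations in section 11.5 belong to the PI and sleep scientist team, whereas section 9.6.1 names a physician and sleep technician team. Overlap is plausible from section 9.7 but not stated.
- **The whole primary outcome is biased.** Only its sleep-structure part is directly exposed; stage durations and awakenings are secondary in section 6.
- **Masking costs no staff time.** No scoring workload or staffing is given. Section 7 provides for four nights per participant, so 15 participants yield 15 × 4 = 60 recordings. Arousal, respiratory and limb-movement indices suggest that stored recordings will be reviewed anyway, but a full offline manual score is not described.
- **The same scorers could simply be given relabelled files.** Someone who watched a night live may recognise it.
- **Automated staging is a clean check.** In the Appendix A examples, night 1 stays on standard settings while night 2 switches with stage. If artefact is visible, it could reveal the condition to a scorer and also disturb an algorithm reading the same EEG.

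**Conclusion.** The concern holds for manually staged outcomes. Followed as written, section 9.5 lets the sleep-structure part of the primary measure and the secondary staging metrics be scored with knowledge of night, pattern and intended effect. Nothing elsewhere in the document prevents this.

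The size is unknown. The figure of about 7-24 minutes rests on an unsourced 2-5% one-directional shift, 30-second epochs and a 6-8 hour night. With no effect size or SD in the plan, it cannot be called large or small. The conclusion rests on the missing safeguard, not on that figure.

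A reader might also infer that masking would make the baseline-versus-stimulation contrast sound. It would not: on the first visit the baseline night always comes first, and that order effect remains.

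**What to change.** Amend section 9.5 and add matching text to section 11.2:

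1. Stimulation delivery and real-time staging are open-label. Real-time staging is not used as the outcome.
2. Manual scores used as outcomes come from stored recordings with date, night label and stimulation log removed, presented in random order.
3. The scorer is an existing team member or a collaborating-site member who did not deliver stimulation to that participant. The data sharing in section 7 already makes the second route possible.
4. State before analysis whether manual or automated staging is primary, and report the same contrast with the other as a sensitivity analysis.
5. Acknowledge that stimulation artefact may partly unmask the scorer and may affect automated staging, so the sensitivity analysis is free of scorer expectation but not of artefact.

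The cost is offline scoring and file-handling time, which the documents do not let us quantify. A new reader is not inherently required. Stimulation, visits and sample size do not change, and the masking can be applied to recordings already stored.

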9.6. Description of study intervention(s), comparators and study procedures (clinical)

9.6.1. Description of study intervention(s)

We will use both an open and a closed-loop approach to investigate sleep perturbations through stimulation deep brain targets. As previously mentioned, FDA approved clinician or patient programmers specific to the implanted device will be used at the open-loop stage, to explore the effect of available stimulation patterns when they are synchronized with different sleep stages. A physician/sleep technician team will be overseeing the delivery of stimuli during real-time sleep scoring on testing nights. See Appendix A. for example stimulation paradigms

9.6.2. Description of comparator(s)

We will use both within- and between-subject comparators. As within-subject comparators, these will primarily be the usual patient settings of low frequency (LF) or high frequency (HF) continuous stimulation (ON) at the clinically prescribed amplitude and frequency. Therefore, we will be able to make assumptions both about these settings (beneficial/disruptive) and the intervention, with regards to effects on EEG patterns, autonomic activity, behavioural measures etc. In addition, since we will be applying a number of exploratory patterns per night (according to sleep stage), each of these will be used as a comparator to others. Where electrical stimulation will be switched off (OFF), this will be compared to individual stimulation configurations as well as all (ON) states. Where comparable stimulation patterns will be used in different patient groups (e.g. HF stimulation during NREMS2 in both HC and ANT), these will serve as between-subject comparators. In addition, given the exploratory nature of this study, the responses of different participants to the same stimulation pattern will be compared (e.g. effects on sleep stages/EEG rhythms of stimulation during REM, between patients with hippocampal electrodes).

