Upon awakening (at a time decided based on the sleep diary), a salivary sample will be obtained for morning cortisol. Participants will complete specific tasks at the time of awaking, and again at 30 minutes and 60 minutes post awaking.. These tasks will consist of the KSS, Mood, KDT, , , and PVT.

During the intervening day, the patients will be allowed to read, watch television, and socialize with caregivers, as well as complete tasks and questionnaires.

Testing/stimulation night:

We will use the programmers in an initial open-loop approach during the first visit, to see if a pattern can help optimize sleep stages and perturb sleep patterns. We will reconfigure each subject with polysomnography system and ensure it is still operating per requirements. The intent is to provide a consistent environment over both nights. We will again capture EEG (and if available, intracranial data). We will use real-time classification of sleep architecture to perturb the networks with variants of stimulation (see tables per target in Appendix A). For the initial sleep cycles, we will be using manual (open loop) interventions by the sleep monitor and the site clinician and scientist. In parallel, the laptop algorithm will be running a prototype closed-loop control to demonstrate the bridge to automated closed loop control. The output of the algorithm and stimulation commands will be logged and compared to the manual interventions.

Upon waking, a salivary sample will be obtained for measuring of early morning cortisol. The cognitive tasks will be performed as listed previously, to assess sleep inertia and other response variables. Subjective questionnaires will be administered post-cognitive screen. Cognitive tests will continue throughout the day to assess variation in the patient's performance.

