9.9. Sample Handling

9.9.1 Sample handling for study purposes

Salivary samples (2mls in a universal container pot) will be obtained for measuring of salivary cortisol levels, for study purposes only. Samples will be obtained upon awakening after each night (e.g. at 6am).

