11.3. Sample Size Determination

This is a feasibility study into recruiting and conducting the study procedures in patient populations. Given the exploratory and novel nature of this study, effect sizes are as of now, unknown. We are collecting from different groups bearing in mind that a minimum n=3 is required for the most rudimentary statistics based on patient number. We therefore expect 15 patients to be the lowest bound for 5 different DBS electrode locations. There will be multiple comparable stimulation epochs per patient, across three nights (second night of first visit and both nights of second visit). The number of sleep stages and cycles per night will vary between participants, with an added unknown being the effect of the disease state on sleep. However, this within- and across-subject comparison will boost statistical power. Further support that an N-of-1 trial design can be used for closed-loop DBS research and provide individualized, precision data to inform device development, was published recently (Stevens and Gilbert 2020).

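### Post-waking and whole-night outcomes reflect a night's whole mixture of stimulation, so they should be analysed by night and not credited to single within-night patterns

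*Combined protocol and SAP*

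**What the plan says.** **Exposure.** Section 9.6.2 sets the patterns against one another: "since we will be applying a number of exploratory patterns per night (according to sleep stage), each of these will be used as a comparator". The sentence just before lists behavioural measures among the effects of interest. Section 9.6.3 also foresees comparing sleep inertia between stimulation conditions.

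**Outcomes.** A secondary objective in section 6 is "Effect of stimulation on sleep inertia and vigilance & performance during the day". For the morning tests, section 9.7 says "Participants will complete specific tasks at the time of awaking, and again at 30 minutes and 60 minutes post awaking", and after the stimulation night "Cognitive tests will continue throughout the day to assess variation". On cortisol, section 9.9.1 says "Samples will be obtained upon awakening after each night (e.g. at 6am"), whereas section 9.6.3 provides for one sample per visit. Number of cycles and sleep efficiency (sections 6 and 7) summarise a night.

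**Analysis.** Section 11.2 states: "We will further assess correlations between stimulation perturbations and observed cognitive measures, physiological biomarkers (cortisol), subjective questionnaires, and post-hoc analysis of sleep patterns". It gives no unit of analysis and no summary of exposure for a night. Section 11.3 looks to repeated epochs for power: "There will be multiple comparable stimulation epochs per patient, across three nights". It does not separate outcomes that have a value for each epoch from those that do not.

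**The concern.** The design has two levels. Stimulation changes within the night, by stage and cycle. The morning and whole-night outcomes come only after, or across, the complete night. The tests at 0, 30 and 60 minutes and those later in the day are repeats, but all follow the same night. They add precision about that night and no contrast between the patterns inside it.

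If section 11.2 is carried out pattern by pattern, one morning's result is set against every pattern delivered the night before. The correlations then rest on far fewer independent results than their count suggests. A pattern that reduces sleep inertia and one that worsens it can also offset each other unseen.

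This matters during the study as well as at the end. Sections 9.8 and 11.5 use first-visit results to guide the second visit. By then each patient has had one stimulation night, so crediting that morning's result to one pattern could steer the second visit wrongly.

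**Working it through.** **The plan's own figure.** Section 11.3: 3 patients × 5 electrode locations = 15. This reproduces. No power formula, effect size or standard deviation is given to check further.

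**Nights and contrasts.** Sections 9.7, 9.8 and 11.3 give 1 baseline night and 3 stimulation nights per patient.
- Per patient: 4 nights, so 4 − 1 = 3 within-patient contrasts.
- Per target at the minimum of 3 patients: 3 × 4 = 12 nights and 3 × 3 = 9 contrasts.
- All 15 patients: 15 × 4 = 60 nights and 15 × 3 = 45 contrasts.

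These are upper limits. If cortisol is taken once per hospital visit, a patient has 2 values and 2 − 1 = 1 contrast.

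**Can pattern effects be separated?** Write the outcome of night j in patient i as y_ij = a_i + Σ_k b_k x_ijk + e_ij. Here x_ijk counts the stage periods in which pattern k was used, and standard stimulation is the reference. After centring within patient, b_k is estimable only if its unit vector lies in the row space of the centred x matrix.

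Appendix A, stimulation night of each example:
- Example 1: N1 off, N2 off, N3 low, REM off, N1 off, N2 low, REM off. Distinct patterns: N1 off, N2 off, N2 low, N3 low, REM off = 5. Against baseline the rank is 1, and 0 of 5 effects are estimable.
- Example 2: N1 off, N2 off, N3 off, REM high = 4 distinct patterns. Rank 1.
- Baseline plus both examples in one patient: 7 distinct patterns, rank 2, 0 of 7 estimable.
- All 15 patients given example 1 on every stimulation night (a limiting case, not the plan): the rank stays 1.

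**A favourable case.** Assume that each stage of each stimulation night is assigned at random to off, low, high or standard, and that effects add up and are equal across patients. There are 4 stages × 3 non-standard states = 12 effects. Averages over 500 simulated allocations:

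| Patients pooled | Within-patient contrasts | Effects estimable, of 12 |
|---|---|---|
| 1 | 3 | 0.2 |
| 3 (minimum per target) | 9 | 2.6 |
| 5 | 15 | 11.5 |
| 15 | 45 | 12 |

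Estimable here means only that a unique estimate exists, not that it is precise.

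**What the night as unit supports.** With four regimens (baseline, open-loop, adaptive, control/off) once each in 3 patients, a block analysis leaves (3 − 1) × (4 − 1) = 6 residual degrees of freedom per target.

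**The case against.** The strongest reply is that the plan never commits to the faulty analysis. The sentence in 9.6.2 names no morning outcome, and that section's example of comparing responses to one pattern concerns sleep stages and EEG rhythms. Usual settings are the primary comparator. Section 6 times the post-waking tests after the baseline night and after intervention, and section 9.7 sets one night against another. Section 11.2 does not define a perturbation as a within-night pattern, and it falls back on trends where formal analysis is impossible.

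Much of this stands. The whole-night contrast is valid, and the documents nowhere say that a morning score will be repeated against each pattern. But 9.6.2 moves directly from behavioural measures to patterns as comparators, and 11.2 leaves the unit open for exactly these outcomes. Exploratory status excuses imprecision. It does not excuse counting one result several times.

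A reader might infer three stronger things, none of which the documents support:
- **That the secondary objectives cannot be answered.** They can, for a night's regimen as a whole.
- **That pattern effects can never be separated.** That is so for the Appendix A examples within a patient. Pooling could separate patterns, but only with a designed allocation and common effects, which the plan does not state.
- **That each stimulation night should hold one fixed stage-to-stimulation map.** Appendix A example 1 itself changes N2 from off to low. On the adaptive night (section 9.8) the algorithm generates the perturbations. A fixed map would still be a mixture across stages.

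**Conclusion.** The point holds for sleep-inertia tests, daytime tests, cortisol, number of cycles and sleep efficiency. At most three contrasts with baseline per patient, and nine per target at the minimum, cannot be attributed to single stage-specific patterns. Epoch counts add no independent information on these outcomes.

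It does not reach stage-specific EEG, microarousals or overnight autonomic data, nor the parts of awakenings and stage durations that can be located in time. In both Appendix A examples stimulation is standard until sleep onset, so sleep-onset latency is not a product of that night's mixture. The primary outcomes are therefore largely untouched.

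The counts for nights and for Appendix A come from the documents. The pooled figures rest on assumed random allocation and on additive, common effects. The whole-night contrasts that remain have limits of their own: the study is unblinded, baseline always comes first, and no randomised night order is stated.

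**What to change.** Change the analysis text only; stimulation delivery stays as it is.

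- **11.2:** Analyse all post-waking and whole-night outcomes with the night as the unit and the night's regimen (baseline, open-loop, adaptive, control/off) as the exposure. Include patient as a random or blocking effect and nest repeated post-waking tests within the night. Drop correlations of individual within-night patterns with these outcomes.
- **9.6.2:** Restrict pattern-against-pattern comparison to outcomes recorded during or just after stimulation.
- **11.3:** State that epoch counts add power only for those outcomes.
- **9.6.3 and 9.9.1:** Reconcile whether cortisol is sampled per visit or per night, since this sets how many contrasts exist.

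The cost is giving up pattern-level conclusions on sleep inertia, daytime vigilance, cortisol and whole-night sleep summaries. No added nights, staff or patients are needed.
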